6.3.8. Dose Modification

Pembrolizumab will be withheld for drug-related haematological and non-haematological of toxicity \geq Grade 3 including laboratory abnormalities, and severe or life-threatening AEs as per Table 7 below.

Toxicity	Hold Treatment For Grade	Timing for Restarting Treatment	Treatment Discontinuation
Diarrhoea/Colitis	2-3	Toxicity resolves to Grade 0-1.	Toxicity does not resolve within 12 weeks of last dose or inability to reduce corticosteroid to 10 mg or less of prednisone or equivalent per day within 12 weeks.
	4	Permanently discontinue	Permanently discontinue
AST, ALT, or	2	Toxicity resolves to Grade 0-1	Toxicity does not resolve within 12 weeks of last dose.

Increased Bilirubin	3-4	Permanently discontinue (see exception below) ¹	Permanently discontinue
Type 1 diabetes mellitus (if new onset) or Hyperglycemia	T1DM or 3-4	Hold pembrolizumab for new onset Type 1 diabetes mellitus or Grade 3-4 hyperglycemia associated with evidence of beta cell failure.	Resume pembrolizumab when participants are clinically and metabolically stable.
Hypophysitis	2-4	Toxicity resolves to Grade 0-1. Therapy with pembrolizumab can be continued while endocrine replacement therapy is instituted	Toxicity does not resolve within 12 weeks of last dose or inability to reduce corticosteroid to 10 mg or less of prednisone or equivalent per day within 12 weeks.
Hyperthyroidism	3	Toxicity resolves to Grade 0-1	Toxicity does not resolve within 12 weeks of last dose or inability to reduce corticosteroid to 10 mg or less of prednisone or equivalent per day within 12 weeks.
	4	Permanently discontinue	Permanently discontinue
Hypothyroidism		Therapy with pembrolizumab can be continued while thyroid replacement therapy is instituted	Therapy with pembrolizumab can be continued while thyroid replacement therapy is instituted.
Infusion Reaction	3-4	Permanently discontinue	Permanently discontinue
Pneumonitis	2	Toxicity resolves to Grade 0-1	Toxicity does not resolve within 12 weeks of last dose or inability to reduce corticosteroid to 10 mg or less of prednisone or equivalent per day within 12 weeks.
	3-4	Permanently discontinue	Permanently discontinue
	3-4	Permanently discontinue	Permanently discontinue
Renal Failure or Nephritis	2	Toxicity resolves to Grade 0-1	Toxicity does not resolve within 12 weeks of last dose or inability to reduce corticosteroid to 10 mg or less of prednisone or equivalent per day within 12 weeks.

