All Other Drug-Related Toxicity²	3 or Severe	Toxicity resolves to Grade 0-1	Toxicity does not resolve within 12 weeks of last dose or inability to reduce corticosteroid to 10 mg or less of prednisone or equivalent per day within 12 weeks.
	4	Permanently discontinue	Permanently discontinue

Note: Permanently discontinue for any severe or Grade 3 drug-related AE that recurs or any life-threatening event.
¹ For participants with liver metastasis who begin treatment with Grade 2 AST or ALT, if AST or ALT increases by greater than or equal to 50% relative to baseline and lasts for at least 1 week then participants should be discontinued.
² Participants with intolerable or persistent Grade 2 drug-related AE may hold study medication at physician discretion. Permanently discontinue study drug for persistent Grade 2 adverse reactions for which treatment with study drug has been held, that do not recover to Grade 0-1 within 12 weeks of the last dose.

Table 8: Dose modification guidelines for drug-related adverse events

If the toxicity does not resolve to Grade 0-1 within 12 weeks after last infusion, trial treatment should be discontinued at the discretion of the investigator. Participants with a laboratory adverse event still at Grade 2 after 12 weeks may continue treatment in the trial only if asymptomatic and controlled. For information on the management of adverse events, see section 7.

Participants who experience a recurrence of the same severe or life-threatening event at the same grade or greater with re-challenge of pembrolizumab should be discontinued from trial treatment.

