6.5.1.5. Management of Infusion Reactions:

Acute infusion reactions (which can include cytokine release syndrome, angioedema, or anaphylaxis) are different from allergic/hypersensitive reactions, although some of the manifestations are common to both AEs. Signs and symptoms usually develop during or shortly after drug infusion and generally resolve completely within 24 hours of completion of infusion. Signs/symptoms may include: Allergic reaction/hypersensitivity (including drug fever); Arthralgia (joint pain); Bronchospasm; Cough; Dizziness; Dyspnea (shortness of breath); Fatigue (asthenia, lethargy, malaise); Headache; Hypertension; Hypotension; Myalgia (muscle pain); Nausea; Pruritis/itching; Rash/desquamation; Rigors/chills; Sweating (diaphoresis); Tachycardia; Tumour pain (onset or exacerbation of tumour pain due to treatment); Urticaria (hives, welts, wheals); Vomiting.

NCI CTCAE Grade	Treatment	Premedication at subsequent dosing
Grade 1 Mild reaction; infusion interruption not	Increase monitoring of vital signs as medically indicated until the participant is deemed medically stable in the opinion of	None

indicated; intervention not indicated	the investigator.	
Grade 2 Requires infusion interruption but responds promptly to symptomatic treatment (e.g., antihistamines, NSAIDS, narcotics, IV fluids); prophylactic medications indicated for < =24 hrs	
Stop Infusion and monitor symptoms.
 
Additional appropriate medical therapy may include but is not limited to:
 
 • IV fluids • Antihistamines • NSAIDS • Acetaminophen • Narcotics 
Increase monitoring of vital signs as medically indicated until the participant is deemed medically stable in the opinion of the investigator.
 
If symptoms resolve within one hour of stopping drug infusion, the infusion may be restarted at 50% of the original infusion rate (e.g. from 100 mL/hr to 50 mL/hr). Otherwise dosing will be held until symptoms resolve and the participant should be pre-medicated for the next scheduled dose.
 
Participants who develop Grade 2 toxicity despite adequate premedication should be permanently discontinued from further trial treatment administration.
	
Participant may be pre-medicated 1.5h (\pm 30 minutes) prior to infusion of pembrolizumab with:
 
Diphenhydramine 50 mg po (or equivalent dose of antihistamine).
 
Acetaminophen 500-1000 mg po (or equivalent dose of antipyretic).

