6.5.3. Supportive Care Guidelines for Pneumonitis

Participants with symptomatic pneumonitis should immediately stop receiving pembrolizumab and have an evaluation. The evaluation may include bronchoscopy and pulmonary function tests to rule out other causes such as infection. If the participant is determined to have study drug associated pneumonitis, the suggested treatment plan is detailed in Table 10.

Study drug associated pneumonitis	Withhold/Discontinue pembrolizumab?	Supportive Care
Grade 1 (asymptomatic)	No action	Intervention not indicated
Grade 2	Withhold pembrolizumab, may return to treatment if improves to Grade 1 or resolves within 12 weeks. Second episode of pneumonitis – discontinue pembrolizumab if upon re-challenge the participant develops a second episode of Grade 2 or higher pneumonitis.	Consider pulmonary consultation with bronchoscopy and biopsy/BAL. Conduct an in person evaluation approximately twice per week Consider frequent Chest X-ray as part of monitoring Treat with systemic corticosteroids at a dose of 1 to 2 mg/kg/day prednisone or equivalent. When symptoms improve to Grade 1 or less, steroid taper should be started and continued over no less than 4 weeks. Consider antibiotics
Grade 3 and Grade 4	Discontinue pembrolizumab	Hospitalise participant

		
Bronchoscopy with biopsy and/or BAL is recommended.
 
Immediately treat with intravenous steroids (methylprednisolone 125 mg IV). When symptoms improve to Grade 1 or less, a high dose oral steroid (prednisone 1 to 2 mg/kg once per day or dexamethasone 4 mg every 4 hours) taper should be started and continued over no less than 4 weeks.
 
If IV steroids followed by high dose oral steroids does not reduce initial symptoms within 48 to 72 hours, treat with additional anti-inflammatory measures. Discontinue additional anti-inflammatory measures upon symptom relief and initiate a prolonged steroid taper over 45 to 60 days. If symptoms worsen during steroid reduction, initiate a re-tapering of steroids starting at a higher dose of 80 or 100mg followed by a more prolonged taper and administer additional anti-inflammatory measures, as needed. Add prophylactic antibiotics for opportunistic infections. The use of infliximab may be indicated as appropriate.

--	--	--

Table 10: Recommended Approach to Handling Pneumonitis

For Grade 2 pneumonitis that improves to \leq Grade 1 within 12 weeks, the following rules should apply:

- First episode of pneumonitis

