 - May increase dosing interval by one week in subsequent cycles
- Second episode of pneumonitis
 - Permanently discontinue pembrolizumab if upon re-challenge participant develops pneumonitis \geq Grade 2

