APPENDIX 4: Identification, evaluation and management of ECIs

ECI	Grade	Action to be taken	Supportive Care
Pneumonitis –	Grade 1 (Asymptomatic)	
 No action 	
 Intervention not indicated
	Grade 2	
 Report as ECI within 24 hours Withhold pembrolizumab, may restart if Grade 1 or resolved within 12 weeks Consider bronchoscopy and biopsy/BAL, ID Consult and frequent chest x-ray for monitoring. Conduct in person evaluation twice a week 	
 1-2mg/kg/day prednisone or equivalent. Symptoms grade 1 or less, initiate steroid taper for no less than 4 weeks. Permanently discontinue pembrolizumab if dose cannot be reduced to 10mg prednisone or less or equivalent per day within 12 weeks.
	Grade 3 and 4	
 Report as ECI within 24 hours Discontinue pembrolizumab Hospitalize patient Bronchoscopy with biopsy and/or BAL is recommended. 	
 methylprednisolone 125mg IV. Symptoms grade 1 or less initiate steroid taper for no less than 4 weeks 
 Prednisone 1 to 2 mg/kg/day or dexamethasone 4mg every 4 hours If IV steroids do not reduce initial symptoms within 48-72 hours treat with additional anti-inflammatory measures. At symptom relief discontinue anti-inflammatory and start steroid taper over 45-60 days. If symptoms worsen during this period refer to ECI guidance document v5.0.
	
 1st episode - May increase dosing interval by one week in subsequent cycles 2nd episode of - Pneumonitis Permanently discontinue pembrolizumab if upon re-challenge patient develops Pneumonitis ≥ Grade 2 		
Colitis	Grade 1 (Asymptomatic)	
 No action 	
 Intervention not indicated
	Grade 2 (For grade 2 diarrhoea that persists > 3 days)	
 Report as ECI within 24 hours Withhold pembrolizumab, may restart if Grade 1 or resolved within 12 weeks Symptomatic treatment Consider GI consult & endoscopy to rule out colitis 	
 Prednisone 1-2mg/kg/day or equivalent Symptoms grade 1 or less, initiate steroid taper for no less than 4 weeks. Permanently discontinue pembrolizumab if dose cannot be reduced to 10mg or less of prednisone or equivalent per days within 12 weeks. If symptoms worsen or persist >1 week treat as grade 3.

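### For a second Grade 2 pneumonitis, the section 6.3.8 table read alone allows a restart, section 6.5.3 and Appendix 4 require a permanent stop, and no text says which governs

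*Combined protocol and SAP*

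**What the plan says.** **Pneumonitis, section 6.3.8.** The dose-modification table has its own Grade 2 pneumonitis row. Treatment is held and may restart at Grade 0-1. The row gives two reasons to discontinue: the toxicity has not resolved within 12 weeks of the last dose, or the steroid cannot be brought down to the stated prednisone level within 12 weeks. Recurrence is handled in the note under the table, "Permanently discontinue for any severe or Grade 3 drug-related AE that recurs or any life-threatening event", and in a closing sentence on re-challenge that is limited to severe or life-threatening events.

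**Pneumonitis, section 6.5.3.** The Grade 2 row of the pneumonitis table also starts with a hold and a possible return to treatment. It then adds a second-episode rule: "discontinue pembrolizumab if upon re-challenge the participant develops a second episode of Grade 2 or higher pneumonitis". The rules under that table repeat it: "Permanently discontinue pembrolizumab if upon re-challenge participant develops pneumonitis" of Grade 2 or higher.

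**Pneumonitis, Appendix 4.** The pneumonitis entry carries the same rule: "2nd episode of - Pneumonitis Permanently discontinue pembrolizumab if upon re-challenge patient develops Pneumonitis ≥ Grade 2".

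**Infusion reactions.** The table in section 6.5.1.5 covers Grades 1 to 4. Its Grade 2 row ends: "Participants who develop Grade 2 toxicity despite adequate premedication should be permanently discontinued from further trial treatment administration". The infusion-reaction row of the 6.3.8 table lists Grades 3-4 only, with permanent discontinuation.

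**The concern.** A site deciding whether to re-dose would naturally open the dose-modification table. For a patient whose Grade 2 pneumonitis has come back on re-challenge and then settled, that table shows a hold followed by a restart. Section 6.5.3 and Appendix 4 say that the same patient stops for good.

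The first issue at stake is safety: whether a patient with recurrent lung toxicity is exposed again could depend on which page was read. The second is consistency. This is an open-label trial planned at 15 to 24 sites. If sites apply different rules, discontinuation counts and pembrolizumab exposure would partly reflect site practice.

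**Working it through.** There is no stated figure to reproduce and no arithmetic applies. The check is a side-by-side reading of the rules for each event.

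**Event A: second episode of Grade 2 pneumonitis on re-challenge**

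| Place | Action | Separates first from later episodes? |
|---|---|---|
| 6.3.8 table, pneumonitis Grade 2 row | Hold; restart at Grade 0-1; stop only on the two 12-week criteria | No |
| 6.5.2, paragraph on immune-mediated pneumonitis | Withhold at Grade 2 | No |
| 6.5.3 table, Grade 2 row | Discontinue on a second episode of Grade 2 or higher | Yes |
| 6.5.3, rules under the table | Permanently discontinue | Yes |
| Appendix 4, pneumonitis | Permanently discontinue | Yes |

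1. *Do the recurrence rules in 6.3.8 close the difference?* The note under the table acts on a recurring severe or Grade 3 event and on any life-threatening event. The closing sentence acts on severe or life-threatening events. The grade table in section 7.2.1.1 calls Grade 2 moderate and Grade 3 severe. A second Grade 2 episode therefore falls outside both rules.
2. *Does footnote 2 of the 6.3.8 table close it?* No. It is attached to the row for all other drug-related toxicity. It concerns intolerable or persistent Grade 2 events, not recurrence after recovery.
3. *Does a cross-reference or precedence rule resolve it?* Section 6.3.8 refers readers to section 7 for adverse event management, but section 7 is pharmacovigilance and holds no re-dosing rule for pneumonitis. Section 6.5.2 leads to Appendix 4, but 6.3.8 leads to neither 6.5.3 nor Appendix 4. No text ranks these sections.
4. *Result.* A second Grade 2 pneumonitis that resolves, with steroids reduced in time, meets no stop criterion in 6.3.8 and meets the permanent-stop criterion in 6.5.3 and Appendix 4. The mismatch is confirmed.

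**Event B: Grade 2 infusion reaction despite adequate premedication**

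| Place | Action |
|---|---|
| 6.5.1.5, Grade 2 row | Permanently discontinue |
| 6.3.8 table, infusion-reaction row | No Grade 2 entry |
| Appendix 4 | No infusion-reaction entry |

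5. At Grades 3-4 the two sections agree. At Grade 2, 6.3.8 is silent, so a site can follow 6.5.1.5 without breaching it.
6. *Result.* This is a missing entry and a missing cross-reference, not two instructions that conflict.

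**The case against.** The best defence is that the pneumonitis sections complement each other. The Grade 2 row in 6.5.3 opens with much the same hold-and-return rule as 6.3.8 and then adds the second-episode condition; Appendix 4 agrees, and nothing in 6.3.8 expressly says that a second episode should be restarted. In addition, section 6.5.2 asks that any immune-related event of Grade 2 or higher be discussed at once with the Chief Investigator or designee. Both points lower the risk. They do not remove it: the complementary reading is written nowhere, the 6.3.8 row is itself specific to event and grade, and 6.5.3 introduces its table as a suggested plan.

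Several stronger readings are tempting but not supported:

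- *That infusion reactions also get opposite instructions.* Silence in 6.3.8 on Grade 2 is neither an instruction to take no action nor one to re-dose.
- *That 6.3.8 rules out action below Grade 3.* The lead-in, "Pembrolizumab will be withheld for drug-related haematological and non-haematological of toxicity" of Grade 3 or above, goes on to defer to the table, and the table lists Grade 2 holds for several toxicities, pneumonitis among them.
- *That the premedication wording contradicts itself.* "the participant should be pre-medicated for the next scheduled dose" applies to reactions that have not resolved within an hour. "Participant may be pre-medicated 1.5h" stands in the general premedication column, which also covers patients whose infusion was restarted. The two largely describe different situations.
- *That the arms would differ in pneumonitis.* Section 6.2.3 permits lung lesions to be irradiated but expects most targets to be skin or superficial nodes. No figure in the documents supports a difference.

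**Conclusion.** The point holds for one event. For a second Grade 2 pneumonitis on re-challenge, the 6.3.8 table read alone permits a restart that 6.5.3 and Appendix 4 exclude, with no stated precedence and a pointer that leads elsewhere. The Grade 2 infusion reaction is a secondary gap in 6.3.8.

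The size cannot be quantified. The documents give no rate for Grade 2 pneumonitis, for recurrence on re-challenge, or for infusion reactions despite premedication, so any patient count would be a guess. Power, alpha and the sample size of 234 are unaffected, and no effect on the primary endpoint is shown. The conclusion rests on a literal reading of the 6.3.8 row and on a site possibly using that table without also consulting 6.5.3. It is a specific, safety-relevant inconsistency that should be corrected, not a flaw in the design.

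**What to change.** 1. Reconcile the 6.3.8 pneumonitis row and its recurrence notes with 6.5.3 and Appendix 4, so that a second Grade 2 episode has one stated action throughout. Alternatively, have the 6.3.8 row defer explicitly to 6.5.3.
2. Add a cross-reference from the 6.3.8 infusion-reaction row to 6.5.1.5.
3. Replace the pointer from 6.3.8 to section 7 with one to the sections that hold the management rules.

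The choice of action belongs to the clinical team; this review takes no view on it. The cost is a wording change, mainly to one table and its notes, processed as a protocol amendment. It needs no extra patients or procedures.

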6.3. Trial Treatment - Pembrolizumab

6.3.1. Investigational Product

The Investigational Medicinal Product (IMP) for this study is Pembrolizumab. A potent and highly-selective humanized mAb of the IgG4/kappa isotype designed to directly block the interaction between PD-1 and its ligands, PD-L1 and PD-L2. Pembrolizumab potentiates existing immune responses only in the presence of antigen and does not non-specifically activate T-cells.

Pembrolizumab will be manufactured by MSD according to Good Manufacturing Practice and will be provided in the formulation as described in Table 6. Additional information about the investigational product can be found in the current Investigator's Brochure (IB).

Product Name & Potency	Dosage Form
Pembrolizumab 50 mg	Lyophilized Powder for Injection

Table 7: Product Description

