Grade 2	May withhold pembrolizumab	Consider systemic corticosteroids in addition to appropriate symptomatic treatment. Steroid taper should be considered once symptoms improve to Grade 1 or less and tapered over at least 4 weeks.
Grade 3 and Grade 4	Withhold pembrolizumab Discontinue if unable to reduce corticosteroid dose to < 10 mg per day prednisone equivalent within 12 weeks of toxicity	Systemic corticosteroids are indicated in addition to appropriate symptomatic treatment. May utilize 1 to 2 mg/kg prednisone or equivalent per day. Steroid taper should be considered once symptoms improve to Grade 1 or less and tapered over at least 4 weeks.
Please Note: If an irAE does not resolve or improve to ≤ Grade 1 within 12 weeks after last administration of pembrolizumab, study therapy discontinuation should be considered after discussion with a Merck Clinical Director via the RM-CTU trial manager..		

Table 9: General Approach to Handling irAEs

Details for managing specific irAEs are summarised below:

Immune-mediated pneumonitis

Monitor participants for signs and symptoms of pneumonitis. If pneumonitis is suspected, evaluate with radiographic imaging. Exclude other causes of pneumonitis, and manage treatment in accordance with the guidelines above. Administer corticosteroids, withhold pembrolizumab for moderate (Grade 2) pneumonitis, and permanently discontinue pembrolizumab for severe (Grade 3) or life-threatening (Grade 4) pneumonitis.

Immune-mediated colitis

Monitor participants for signs and symptoms of colitis. Exclude other causes of colitis, and manage treatment in accordance with the guidelines above. Administer corticosteroids, withhold pembrolizumab for moderate (Grade 2) or severe (Grade 3) colitis, and permanently discontinue pembrolizumab for life-threatening (Grade 4) colitis.

Immune-mediated hepatitis

Monitor participants for changes in liver function (at the start of treatment, periodically during treatment and as indicated based on clinical evaluation) and symptoms of hepatitis. Exclude other causes of hepatitis, and manage treatment in accordance with the guidelines above. Administer corticosteroids and, based on severity of liver enzyme elevations, withhold or discontinue pembrolizumab.

Immune-mediated nephritis

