	Grade 3	
 Report as ECI within 24 hours Withhold Pembrolizumab Consider dermatology consultation and biopsy for diagnosis. 	
 1mg/kg/day prednisone or equivalent or dexamethasone 4mg 4xday. Symptoms grade 1 or less initiate steroid taper for no less than 4 weeks. Permanently discontinue pembrolizumab if dose cannot be reduced to prednisone 10mg or less or equivalent per day within 12 weeks.
	Grade 4	
 Report as ECI within 24 hours Discontinue pembrolizumab Dermatology consultation Consider biopsy for diagnosis & clinical photographs 	
 Initiate steroids starting with 1-2mg/kg prednisone or equivalent.. Symptoms grade 1 or less, initiate steroid taper for no less than 4 weeks.
Other: Myocarditis Pericarditis Pancreatitis Any additional Grade 3 or higher event which the physician considers to be immune related	Grade 2 or Grade 1 that do not improve with symptomatic treatment.	
 Report as ECI within 24 hours Withhold Pembrolizumab Consider biopsy for confirmation of diagnosis. 	
 Systemic corticosteroids may be indicated. If so: Treat with systemic corticosteroids at a dose of 1 to 2 mg/kg prednisone or equivalent once per day. When symptoms improve to Grade 1 or less, steroid taper should be started and continued over no less than 4 weeks. Permanently discontinue for inability to reduce corticosteroid dose to 10 mg or less of prednisone or equivalent per day within 12 weeks. Otherwise, pembrolizumab treatment may be restarted and the dose modified as specified in the protocol
	Grade 3	
 Report as ECI within 24 hours Withhold Pembrolizumab 	
 Treat with systemic corticosteroids at a dose of 1 to 2 mg/kg prednisone or equivalent once per day. When symptoms improve to Grade 1 or less, steroid taper should be started and continued over no less than 4 weeks. Permanently discontinue for inability to reduce corticosteroid dose to 10 mg or less of prednisone or equivalent per day within 12 weeks. Otherwise, pembrolizumab treatment may be restarted and the dose modified as specified in the protocol

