	Grade 4	
 Report as ECI within 24 hours Discontinue Pembrolizumab 	
 Treat with systemic corticosteroids at a dose of 1 to 2 mg/kg prednisone or equivalent once per day.

To be left blank

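### Two pembrolizumab stopping rules disagree: unlisted drug-related Grade 4 immune events (6.5.2 against 6.3.8 and Appendix 4) and Grade 3 enterocolitis (6.5.1.1 against 6.3.8, 6.5.2 and Appendix 4)

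*Combined protocol and SAP*

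**What the plan says.** **Unlisted Grade 4 immune-related events.** The general table in 6.5.2 gives Grades 3 and 4 a single action: "Withhold pembrolizumab Discontinue if unable to reduce corticosteroid dose to < 10 mg per day prednisone equivalent within 12 weeks of toxicity". A line above the table limits it to immune-related events that the protocol does not deal with elsewhere. Later in 6.5.2, drug-associated immune-related events of clinical interest are referred to Appendix 4.

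The dose-modification table in 6.3.8 ends with a catch-all row for other drug-related toxicity. It holds treatment at Grade 3 and permanently discontinues at Grade 4. The note beneath adds: "Permanently discontinue for any severe or Grade 3 drug-related AE that recurs or any life-threatening event". Appendix 4 has an Other category that covers "Any additional Grade 3 or higher event which the physician considers to be immune related". Its Grade 3 action is to withhold; its Grade 4 action is "Report as ECI within 24 hours Discontinue Pembrolizumab".

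**Grade 3 enterocolitis.** Section 6.5.1.1 permanently discontinues pembrolizumab for severe (Grade 3) enterocolitis. The colitis entries in 6.3.8, 6.5.2 and Appendix 4 all hold treatment at Grade 3 and stop it at Grade 4. Section 7.4 lists enterocolitis under the colitis heading.

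**The concern.** Each of these sections tells a site whether a participant may receive pembrolizumab again. The merged row in 6.5.2 makes discontinuation depend on a failed steroid taper. A site using that table alone could therefore conclude that treatment may resume after an unlisted life-threatening reaction once steroids are down, although two other parts of the protocol end treatment. In the enterocolitis case the clash is between two event-specific rules at the same grade. One participant would be taken off the drug for good under 6.5.1.1 and could be restarted under the other three places. What is at stake is participant safety and consistent handling across the 15 to 24 planned sites.

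**Working it through.** No arithmetic applies, so the instructions are set side by side.

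**(a) Drug-related immune event with no named row**

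| Place | Grade 3 | Grade 4 |
|---|---|---|
| 6.5.2 general table | Withhold; discontinue if taper fails | Same as Grade 3 |
| 6.3.8 catch-all row | Hold until Grade 0-1 | Permanently discontinue |
| 6.3.8 note | Stop if the event recurs | Stop, as life-threatening |
| Appendix 4, Other | Withhold | Discontinue |

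Section 7.2.1.1 defines Grade 4 as life-threatening, so the 6.3.8 note applies to it. On a first Grade 3 event every place says hold. The disagreement is confined to Grade 4.

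Three pieces of text bear on which instruction governs.

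1. The opening sentence of 6.3.8 sends toxicity of Grade 3 or above to its own table, "including laboratory abnormalities, and severe or life-threatening AEs as per Table 7 below". This favours discontinuation. The table number is off, since the caption of the table meant is "Table 8: Dose modification guidelines for drug-related adverse events" and Table 7 is captioned "Table 7: Product Description", but the position makes the target clear.
2. The scope line of the 6.5.2 table also favours discontinuation. The protocol does not say whether a catch-all row elsewhere counts as dealing with an event. If it does, the Grade 4 half of the 6.5.2 row has no evident use for drug-related events. If it does not, the conflict stands. The row needs editing on either reading.
3. The referral to Appendix 4 relies on the list in 7.4. The last entry there is worded for Grade 3 events, whereas Appendix 4 covers Grade 3 or higher.

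The steroid threshold also differs: below 10 mg per day in 6.5.2, and 10 mg or less in 6.3.8 and Appendix 4. These differ only at exactly 10 mg.

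**Consequence for the fix.** The 6.3.8 note has no exception, yet named endocrine rules allow treatment to continue or resume at Grade 4:

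- hypophysitis (6.3.8, Appendix 4);
- new-onset type 1 diabetes or Grade 3-4 hyperglycaemia once stable (6.3.8);
- hypothyroidism on replacement (6.3.8, Appendix 4);
- endocrinopathy that has resolved and is controlled on hormones (6.5.2).

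Grade 4 hyperthyroidism is a permanent stop in both 6.3.8 and 6.5.2.

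**(b) Grade 3 enterocolitis or colitis**

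| Place | Grade 3 | Grade 4 |
|---|---|---|
| 6.5.1.1 (enterocolitis) | Permanently discontinue | No bullet |
| 6.3.8 (diarrhoea/colitis) | Hold | Permanently discontinue |
| 6.5.2 (colitis) | Withhold | Permanently discontinue |
| Appendix 4 (colitis) | Withhold | Discontinue |

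Because 7.4 treats enterocolitis as a form of colitis, both rules apply to the same event, and no scope line separates them.

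**The case against.** The strongest reply to (a) is that the 6.5.2 table yields by its own terms: an unlisted drug-related Grade 4 event is covered by the 6.3.8 catch-all row and by Appendix 4. That is the more natural reading, and it keeps the point small. It does not save the row, whose Grade 4 content would then be either redundant or misleading.

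A reader might infer that 6.5.2 permits restart after a life-threatening event. The row gives no such permission and no restart criteria. Restart timing is in 6.3.8, where the Grade 4 catch-all entry is a permanent stop. The row implies resumption only through its conditional form.

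A reader might also infer from 7.4 that unlisted Grade 4 events fall outside Appendix 4. That is strained: the heading over that group classes its events as of clinical interest at any grade, and Appendix 4 has a Grade 4 action. The wording deserves tidying, no more.

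The 6.3.8 re-challenge sentence refers to "recurrence of the same severe or life-threatening event at the same grade or greater with re-challenge of pembrolizumab should be discontinued". It might be read as accepting restart after any life-threatening event. It is a stop rule and grants nothing, and it has a proper use where an endocrine rule allows resumption.

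Safeguards also count. Immune-related events of Grade 2 or higher go at once to the chief investigator or designee. Symptomatic events of clinical interest stop drug immediately, and management questions go to the sponsor. These make a wrong restart less likely, but they do not say which instruction applies.

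Against (b) no comparable reply is available.

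**Conclusion.** Both inconsistencies are in the current text, and both are minor and limited to wording. Point (a) is narrow: it concerns only drug-related Grade 4 immune events without their own row, and the surrounding text already leans towards discontinuation. Point (b) is the clearer contradiction.

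No frequency can be attached to (a). The nearest figure in 6.5.2, under 1% of about 5000 participants for uveitis and severe skin reactions, concerns events that have their own rows in Appendix 4.

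A reader might infer that the trial's results are at risk. The documents do not support that. The sample size in 8.2 and the efficacy analyses in 8.4 and 8.5 do not depend on these rules, and the Grade 3-5 toxicity comparison in 8.5 concerns the occurrence of an event, not the dosing decision after it.

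The conclusion assumes that the sponsor means the Grade 4 stop in 6.3.8 and Appendix 4 to hold. The right action for Grade 3 enterocolitis is a clinical decision for the sponsor's safety lead.

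**What to change.** - **6.5.2 general table:** split the row. Grade 3: withhold, and permanently discontinue if steroids cannot be reduced to 10 mg or less of prednisone or equivalent per day within 12 weeks. Grade 4: permanently discontinue, as in 6.3.8 and Appendix 4.
- **6.3.8 note:** add an exception where a named endocrine row or rule allows continuation or resumption. Grade 4 hyperthyroidism remains a permanent stop.
- **7.4, last entry:** extend it from Grade 3 to Grade 3 or higher.
- **6.5.1.1:** withhold at Grade 3 and permanently discontinue at Grade 4, matching 6.3.8, 6.5.2 and Appendix 4. If the safety lead prefers the stricter Grade 3 stop, change those three places instead.

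Two further edits may look attractive and should not be made. A sentence ranking 6.3.8 above other catch-all rows could let its footnote on Grade 2 events, which leaves holding to the physician's discretion, displace the Appendix 4 instruction to withhold for Grade 2 myocarditis, pericarditis or pancreatitis. The re-challenge sentence in 6.3.8 should also stay as it is, because narrowing it would weaken a stop rule.

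The cost is a wording amendment to four sections, with no added participants, visits or procedures.
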